12.6 VFSS Stopping Rules

- If the PAS is equal to or greater than 6 on 3 consecutive bolus trials of the same consistency, that consistency should be stopped and the investigator (or trained and authorized designee) can decide if it is safe to move to the next consistency or if the study needs to be stopped.
 - Penetration Aspiration Score Definitions:
 - 6: Material enters the airway, passes below the vocal folds, and is ejected into the larynx or out of the airway.
 - 7: Material enters the airway, passes below the vocal folds & is not ejected from the trachea despite effort
 - 8: Material enters the airway, passes below the vocal folds & no effort is made to eject
- A 'Stop' may be applied at any time if the Investigator (or trained and authorized designee) feels it is unsafe for the patient to continue.
- If VFSS time exceeds 3 minutes the procedure must be stopped.

If the VFS procedure is stopped due to any of these Stopping Rules, the 1 day follow-up visit must still be completed.

12.7 Post-Exam

After completion of all study-related testing, the site will stop the recording on the study computer and follow specified procedures for saving and uploading all study files to a secure transmission to the CRO as per the Study Manual.

Subsequently, the site will follow their institution's standard of care for further assessing swallowing impairment in subjects with suspected dysphagia.

Follow-up with the study subject will be performed within 2 business days following completion of all the exams to collect data on AEs. If the subject is still hospitalized at this time, this data will be collected via an in-person interview. If the subject has been discharged at the time of follow-up, this data will be collected via a telephone interview.

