- Prevalence of impaired swallowing safety and efficiency of the swallows of thin (THIN-Ba) and thickened stimuli as determined by VFSS at bolus and patient level by the following predetermined subgroups: stroke, other neurological diseases, other patients.
- Timing and Outcome of the dysphagia screening as per usual care protocol of the study site
- Timing and Outcome of the dysphagia Clinical Swallow Assessment (CSE) by SLP (speech language pathologist) where applicable as per usual care protocol of the study site
- Impact of VFSS results on Nutritional Management
- DDS accuracy in terms of AUC, sensitivity and specificity by sub-group (Stroke, Other Neurological Diseases and Others) for swallow safety and efficiency problems for all consistencies (THIN-Ba, MILD-Ba, MOD-Ba)

Safety Endpoints

All adverse events (AEs) will be observed during and within two business days following the study procedure.

TRIAL DESIGN

An operationally seamless single-arm, prospective, multicenter, single-blinded for central outcomes assessors trial to test DDS in assessing swallowing safety and efficiency in patients at risk of oropharyngeal dysphagia. The study is designed as operationally seamless to facilitate the updating of the threshold on the ROC curve for swallowing safety if required and to validate the DDS classifier with a fixed threshold using an independent validation set.

The study has been planned to enroll and study approximately 900 patients (maximum enrollment 1300) with the possibility of early stopping for futility or success.

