During an assessment, a patient takes a series of sips as directed by a clinician. Each sip is processed and transferred to the application software on the PC. The data are stored and then sent to the CRO. These data are subsequently analyzed and the system outputs an assessment of swallowing safety and efficiency.

STUDY DURATION

This study is expected to require approximately 18 months to complete.

TRIAL VISITS

Consent must be obtained prior to the study procedure (up to 2 weeks prior). The study procedure of simultaneous VFSS and DDS measurement will be completed in one day and the subject will be followed within 2 business days after the study procedure to monitor for adverse events. The sequence of Study Procedures is described in the Table 1.

STATISTICAL METHODS

Success criteria and hypothesis testing

The success criteria for the DDS device validation trial is that the sensitivity is greater than 80% with a specificity greater than 50%. Here the sensitivity and the specificity will be estimated using an independent validation dataset. Thus the following one-sided hypothesis testing will be carried out:

$$H_0: H_0^{se} \cup H_0^{sp}$$
 vs.

$$H_A: H_A^{se} \cap H_A^{sp}$$

Where

 H_0^{se} : Sensitivity ≤ 0.8 ; H_A^{se} : Sensitivity > 0.8; H_0^{sp} : Specificity ≤ 0.50 ; H_A^{sp} : Sensitivity > 0.50

The same hypothesis test as above will be applied to the secondary endpoints. If the primary hypothesis meets statistical significance then hypothesis testing for secondary endpoints will be carried out in a hierarchical fashion to ensure that the type-I error is controlled at the 2.5% level (one-sided).

Threshold optimization

The validation trial will start with the frozen classifier based on a fixed threshold derived using the ROC curves obtained using the 10,000 test datasets following a random splitting (80:20) of the Phase-0 data.

At the first interim, sensitivity and specificity will be calculated based on the fixed threshold. If the Area under the ROC curve at the first interim is above 75% but the sensitivity and/or specificity are low then the threshold will be revised based on the first interim data. In this case, the validation will exclude the data used for the first interim, i.e. the validation trial will start with the first patient enrolled after the first interim analysis data cut-off date. In case the fixed threshold from the phase-0 data is not revised using the first interim data, the trial continues as planned.

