6 TRIAL PLAN

Table 1: Sequence of Study Procedures

Stud	ly Pro	ced	ures
------	--------	-----	------

Written informed consent

Inclusion/exclusion criteria review

Schedule VFSS with simultaneous DDS

Prepare all swallowing substances and portion into cups: thin barium, and mildly and moderately -thick barium using a mixture of TUC and barium (can be done in advance as per study manual instructions)

Swallow Exam of up to 5 sips of thin barium simultaneously recorded using both the VFSS and DDS

Swallow Exam of up to 4 boluses of mildly-thick barium simultaneously recorded using both the VFSS and DDS

Swallow Exam of up to 4 boluses of moderately-thick barium simultaneously recorded using both the VFSS and DDS

Upload the subject's study files (VFSS recording, DDS signal recording, acoustic soundtrack recording to a secure site for retrieval from the Sponsor or designee.

AE assessment within 2 business days following the study procedure

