8.6 Safety endpoints

All adverse events (AEs) will be observed from the time the consent form is signed through the exit of the subject from the study.

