15.1.4 Anticipated Adverse Events

AEs that are anticipated to occur during this clinical trial are believed to be consistent with those associated with underlying disease and/or dysphagia screening tests and VFSS or have been identified by the Sponsor as part of their risk assessment. Anticipated AEs include and are not limited to, the following:

- Choking episode or airway obstruction event requiring emergency response
- Fever
- · Congestion and/or shortness of breath
- Chest pain
- Anaphylactic reaction (allergy to the test stimuli)
- New diagnosis of respiratory infection
- Nausea and/or Constipation

Potential AEs that may be specifically related to the investigational device (accelerometry device) include, but are not limited to, the following:

- Allergy, skin reaction, or irritation to the adhesive used for the sensor fixation
- Infection
- Discomfort
- Electrical shock
- Electromagnetic (EM) emission interference with other devices leads to failure of life supporting device*

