3.12.6 Safety Analysis

All safety analysis will be performed on the Safety Analysis Set. All adverse Events (AEs) will be coded using the Medical Dicotionary for Regulatory Agencies (MedDRA). A TEAE is defined as an AE that starts or worsens on or after study Day 1 (defined as the procedure day), and no more than XX days after the procedure. All TEAEs will be listed by subject number and MedDRA coding.

The number and percentage of subjects with TEAE will be summarized in several different tables:

- All TEATs by System Organ Class (SOC) and preferred term (PT)
- Study procedure related AEs by SOC and PT
- Severity of All TEAEs by SOC and PT.

A subject with 2 or more AEs within the same level of the MedDRA term will be counted only once in that level using the most extreme incident (most severe for the severity table and related for the relationship to study procedure table).

4 Blinding and Firewall for Interim Analysis

The key blinding required for this trial is the blinding of the sites to the VFSS results determined by a central VFSS laboratory and the blinding of the central VFSS laboratory to the yet-to-be validated results from the DDS available at the sites. There will be no communication between the sites and the central laboratory. The results of the VFSS on each subjects' boluses will be kept blinded and would not be available to the sites or the sponsors. It will be made available to the iDMC and the iSC members with the unblinded role through a secured firewall system immediately prior to the time of the interim and the final analyses. The details will be pre-specified in the study protocol as well as in the DMC charter.

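### The only scheduled adverse-event contact has a latest time but no earliest time, and the passages defining the AE window disagree, so AE rates and durations rest on unequal observation times.

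*Protocol*

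**What the plan says.** **Timing of the contact.** Protocol 12.7: "Follow-up with the study subject will be performed within 2 business days following completion of all the exams to collect data on AEs". It is done in person if the subject is still in hospital, otherwise by telephone. The last row of Table 1 (Protocol 6) reads "AE assessment within 2 business days following the study procedure", and the synopsis says "the subject will be followed within 2 business days after the study procedure to monitor for adverse events". No later visit or call is listed.

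**After a stopped exam.** Protocol 12.6 says that "the 1 day follow-up visit must still be completed".

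**Period of AE observation.** The synopsis safety endpoint reads "All adverse events (AEs) will be observed during and within two business days following the study procedure". Protocol 8.6 instead runs "from the time the consent form is signed through the exit of the subject from the study", and Protocol 15, 15.1.1 and SAP 2.5 agree with 8.6. Exit is not defined. Protocol 15.2.1 ends the reporting of serious events at the last trial visit.

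**Analysis.** SAP 3.12.6 counts treatment-emergent events from the procedure day "and no more than XX days after the procedure". SAP 3.8 reports the proportion of subjects with each event and the mean (SD) duration, possibly by disease group or site.

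**The concern.** The synopsis describes a two-business-day observation period, but a call on the afternoon of the exam meets the contact rule. Whatever begins between that call and the end of the period has no scheduled route into the database. Protocol 15.1.4 lists anticipated events that need not be present at the time of an early call, among them "New diagnosis of respiratory infection".

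Three things are at stake:

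- The proportions in SAP 3.8 and 3.12.6 would pool subjects observed for hours with subjects observed for days, and would lean low for events with delayed onset.
- Non-serious events still ongoing at the contact have no required later follow-up, so their durations are cut at a time that depends on the site. In a by-site table, calling habits could look like safety differences.
- With the cut-off for treatment-emergent events blank, it could be set after data exist. The monitoring committee sees AE data at the interims and may recommend stopping on them (SAP 3.11.3).

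**Working it through.** The plan gives no figure to reproduce. There are three checks.

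**1. How long may a compliant site observe a subject?** Inputs: the two-business-day limit (Protocol 12.7, Table 1, synopsis) and the absence of any minimum. The exam day is day 0 and holidays are ignored.

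| Exam day | Latest compliant contact | Calendar days |
|---|---|---|
| Monday | Wednesday | 2 |
| Tuesday | Thursday | 2 |
| Wednesday | Friday | 2 |
| Thursday | Monday | 4 |
| Friday | Tuesday | 4 |

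The earliest compliant contact is on day 0 for every weekday. The range is therefore from a few hours to 4 calendar days, depending on site habit and weekday.

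**2. How strongly does the recorded share depend on contact time?** The documents give no onset times, so this is an illustration and not an estimate. Assume exponential onset with median m days. The share of events with onset by time t is F(t) = 1 − 0.5^(t/m).

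| m (assumed) | F(1 day) | F(2 days) | F(4 days) |
|---|---|---|---|
| 1 | 0.50 | 0.75 | 0.94 |
| 2 | 0.29 | 0.50 | 0.75 |
| 3 | 0.21 | 0.37 | 0.60 |
| 5 | 0.13 | 0.24 | 0.43 |

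The relevant quantity is the share of events starting inside the window that a 1-day contact would see.

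- Two-day window, F(1)/F(2): 0.500/0.750 = 67% for m = 1, and 0.129/0.242 = 53% for m = 5.
- Four-day window, F(1)/F(4): 0.500/0.938 = 53% for m = 1, and 0.129/0.426 = 30% for m = 5.

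Contact at the close of the window sees all of them by construction. Events starting later, 1 − F(2) = 25% to 76% or 1 − F(4) = 6% to 57% over the same medians, are missed either way.

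**3. Do the passages agree?**

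| Item | Passage A | Passage B |
|---|---|---|
| Time of contact | Any time up to two business days (12.7, Table 1, synopsis) | 1 day, after a stop (12.6) |
| Start of the contact clock | Completion of all exams (12.7), which fits a stopped exam poorly | The study procedure (Table 1, synopsis) |
| Start of AE observation | The procedure (synopsis) | Consent (8.6, 15, SAP 2.5), up to 2 weeks earlier |
| End of AE observation | Two business days (synopsis) | Exit, undefined (8.6, 15, SAP 2.5) |
| End for tabulation | Not stated in the protocol | XX days (SAP 3.12.6) |

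Protocol 15.2.2 does not close the gap. It follows serious and unanticipated device events already known until they resolve or stabilise, and does not look for new ones.

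**The case against.** **The conflict is smaller than a count of passages suggests.** A reader might infer from 12.6 that subjects stopped for repeated high PAS scores fall under a separate 1-day rule. The text does not support that. The sentence says the visit must still take place, which points to the same single visit every subject has. The amendment summary shows follow-up wording of about one day being standardised to two business days elsewhere, and 12.6 is not among the listed changes. It is most likely a leftover phrase, and a next-day contact meets both rules. This stands, although the current text still needs aligning.

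**Closure at the contact is inferred.** No passage says the contact ends AE collection. The inference rests on no later contact being scheduled. An inpatient's later event might be noticed in routine care, but no passage requires the site to look for it. The part that stands is that exit is undefined.

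**The number missed is unknown.** A reader might take the introduction's 37% pneumonia figure as a measure of missed events. It describes stroke patients who develop aspiration and is neither a rate for the study's boluses nor a rate of late onset. The shares in the working come from assumed medians only.

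**XX matters within limits.** If nothing is collected after about 4 days, any XX of 4 or more changes little. SAP 1 also says the plan is finalised before database lock and unblinding. Both points are fair, but the figure is still blank, and a smaller value would change the tables.

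**Consequences are modest.** This is a single-arm accuracy study with descriptive AE tables. SAP 3.11.3 records a non-significant-risk determination, and Protocol 16.3 reports no related serious events in more than 300 earlier subjects. This stands and limits the weight of the point.

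**Conclusion.** The point holds as a worthwhile, low-cost correction. From the text alone, the one scheduled AE contact has no minimum time, compliant observation runs from a few hours to 4 calendar days, and the passages on AE timing do not agree. AE proportions and durations would therefore rest on unequal observation, with a downward lean for events that start after an early contact but inside the stated period.

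The size in missed events cannot be derived from the documents. The 4-day figure assumes no holidays. That nothing is captured after the contact is an inference from the absence of any later scheduled contact. The documents do not show a deliberate separate rule for stopped exams, nor that respiratory infections in particular will be lost. The sensitivity and specificity analysis is untouched.

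**What to change.** - Reconcile Protocol 12.6, 12.7, 8.6, 15, the synopsis and SAP 3.12.6 to one AE window with a stated start and end, the same for stopped and completed exams. The length is the sponsor's choice; none is proposed here.
- Hold the existing single interview at the close of that window, with a short stated allowance. Without an upper limit, observation time would again vary by site.
- Define study exit as that contact.
- Enter the matching figure for XX in SAP 3.12.6 before the first interim analysis.

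The cost is wording in both documents and no additional contact. A few more subjects will have been discharged and need a telephone call, or will not be reached. The change makes observation comparable between subjects. It does not capture events that start after the chosen window.

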12.8 Premature trial termination

Should it prove necessary to discontinue the trial prior to completion, the Sponsor will notify the Investigators and the appropriate entities including the IRB/IEC. All relevant trial documentation will be returned to the Sponsor. The investigational device will be sent back.

12.9 Trial completion

After trial completion or termination the Investigator will inform the IEC/IRB of the end of the trial.

13 DATA MANAGEMENT

13.1 Data capture

Data collected by the sites will be entered from the source document into an electronic Case Report Forms (eCRF) within a Title 21 CFR Part-11 compliant Electronic Data Capture system (EDC). Data should be entered in eCRFs within 7 days after the subject's visit.

eCRFs must be signed electronically by the Investigator.

13.2 Access rights

Designated site personnel will create a unique username and password and will be required to request access to the database. Once the site personnel are trained access will be approved and the site personnel will have access the eCRF database. This username/password pair may be used by a single individual only; passwords must not be shared with any other person.

13.3 Coding

The following types of data will be coded using standard dictionaries detailed below.

Type of data	Dataset	Dictionary
Adverse Events	AE	MedDRA
Serious Adverse Events	AE	MedDRA

13.4 Database Lock

Clinical database will be locked after review, query resolution, signatures of the eCRF and determination that clinical database is ready for analysis.

Once the Trial is finished and database is locked, the Clinical Data Manager should follow the database unlock/relock process to document any further change.

14 STATISTICS

14.1 Background

The DDS classifier was built using data from around 300 subjects in a proof-of-concept trial using different bolus consistencies: thin barium (THIN-Ba), mildly thick barium (MILDBa) and moderately thick barium (MOD-Ba).

This pivotal trial aims at validating the Dysphagia Detector System (DDS) with respect to the Video-fluoroscopy test (gold-standard) in detecting swallow safety and efficiency impairments. The core component of the DDS is a statistical classifier algorithm that is able to predict the probability that a swallow was normal or with impaired safety and/or impaired efficiency based on the swallow signals captured using a dual-axis accelerometer sensor.

14.2 Success criteria and hypothesis testing

The success criteria for the DDS device validation trial is that the sensitivity is greater than 80% with a specificity greater than 50%. Here the sensitivity and the specificity will be estimated using an independent validation dataset. Thus the following one-sided hypothesis testing will be carried out:

$$H_0\colon H_0^{se}\ \cup\ H_0^{sp}\ \mathrm{vs}.$$

$$H_A\colon H_A^{se}\ \cap\ H_A^{sp}$$

Where

$$H_0^{se}$$
: Sensitivity ≤ 0.8 ; H_A^{se} : Sensitivity > 0.8 ; H_0^{sp} : Specificity ≤ 0.50 ; H_A^{sp} : Sensitivity > 0.50

The same hypothesis test as above will be applied to the secondary endpoints. Hypothesis will be carried out in a hierarchical fashion to ensure that the type-I error is controlled at the 2.5% level (one-sided).

14.3 Threshold Optimization

The validation trial will start with the frozen classifier based on a fixed threshold derived from the Phase-0 (exploratory) trial data.

At the first interim analysis, sensitivity and specificity will be calculated based on the fixed threshold.

If the Area under the ROC curve at the first interim is above 75% but the sensitivity and/or specificity are low then the threshold will be revised based on the first interim data. In this case, the validation will exclude the data used for the first interim, i.e. the validation trial will start with the first patient enrolled after the first interim analysis data cut-off date. In case the fixed threshold from the phase-0 data is not revised using the first interim data, the trial continues as planned.

Power analysis using simulations (described in statistical plan) show the impact of prevalence on power. The targeted prevalence of swallow safety problems using THIN-Ba (primary endpoint) is between 0.3 and 0.4. Throughout the course of the trial prevalence of swallow safety and efficiency problems will be monitored closely by the Data Monitoring Committee (DMC) in a blinded fashion. The study population should be representative of the device intended use population (at risk of dysphagia). According to the published Literature, estimated prevalence of dysphagia in the target population varies from 20-50%. The necessity to carry out VFSS may result in sites selecting patients at higher risk than in the intended target population (such as those already assessed by SLPs). We therefore blindly monitor the prevalence and retrain sites as necessary in order to ensure that they recruit at-risk patients (not only those already assessed as dysphagic by SLPs)

14.4 Sample size calculations

The power and the sample size to test the hypothesis depends on several unknown parameters:

- 1. Subject level prevalence;
- 2. The prevalence of impaired swallows conditional on subject having Dysphagia;
- 3. The true sensitivity and specificity of the DDS device in detecting swallow impairment; and
- 4. The optimum threshold on the ROC curve.

Based on estimates from the exploratory study data, if the DDS is assumed to have a sensitivity and specificity of at least 86% and 60% respectively and approximately 35% patients show impaired safety, then a power of 90% can be achieved with 700 to 800 subjects under a fixed design. Considering that data from additional 100 to 200 subjects may be used for threshold calibration, the starting sample size is 900 subjects. A sample size re-estimation will be carried out at the last interim analysis.

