3.1 Success Criteria and Hypothesis Testing

The success criteria for the DDS device validation trial is that the sensitivity is greater than 80% with a specificity greater than 50%. The sensitivity and the specificity will be estimated using an independent validation dataset. The following one-sided hypothesis testing will be carried out:

$$H_0 : H_0^{se} \cup H_0^{sp} \text{ vs.}$$

$$H_A : H_A^{se} \cap H_A^{sp},$$
(1)

where,

 $\begin{array}{lll} H_0^{se} & : & \mathrm{Sensitivity} \leq .8, \\ H_A^{se} & : & \mathrm{Sensitivity} > .8, \\ H_0^{sp} & : & \mathrm{Specificity} \leq .5, \text{ and} \\ H_A^{sp} & : & \mathrm{Specificity} > .5. \end{array}$

Each of H_0^{se} vs. H_A^{se} and H_0^{sp} vs. H_A^{sp} will be tested at one-sided 2.5% level of significance which will (conservatively) preserve the over-all type-I error for testing H_0 vs. H_A .

The same hypothesis test as in (1) will be applied to the secondary endpoints. Hypothesis will be carried out in a hierarchical fashion to ensure that the type-I error is controlled at the one-sided 2.5% level.

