3.2 Determination of Sample Size

The power and the sample size to test the hypothesis depends on several unknown parameters:

- 1. Subject level prevalence;
- 2. The prevalence of impaired swallows conditional on subject having Dysphagia;
- 3. The true sensitivity and specificity of the DDS device in detecting swallow impairment; and
- 4. The optimum threshold on the ROC curve.

Based on estimates from the exploratory study data, if the DDS is assumed to have a sensitivity and specificity of at least 86% and 60% respectively and approximately 35% patients show impaired safety, then a power of 90% to test H_0 vs. H_A (from equation (1)) can be achieved with 700 to 800 subjects under a fixed design. Considering that data from additional 100 to 200 subjects may be used for threshold calibration, the starting sample size is 900 subjects. A sample size re-estimation will be carried out at the last interim analysis. The maximum sample size is set to 1300 (see Table 5-2).

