3.10 Statistical Considerations

3.10.1 General Statistical Considerations

All statistical analyses and data summaries are to be generated according to this SAP. Any deviations from this SAP will be documented in the Statistical Report and the CSR.

All statistical tests for the efficacy outcomes will be performed at one-sided 2.5% significance level, unless otherwise stated.

Summary statistics will be presented for the overall population as well as stratified by disease group and by site where appropriate.

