5.1 Simulations with Sample Size Re-estimation

Simulations for the proposed GSD with SSR in Section 5 were carried out under the null hypothesis (sensitivity $\leq .8$ and/or specificity $\leq .5$) while varying the prevalence from 35% to 65%. Power from 10,000 monte-carlo runs for different combinations of sensitivity and specificity in Table 8-1 show that the type-I error is preserved at the 2.5%.

Simulations under the alternative (sensitivity > .8 and specificity > .5 for the primary and the first two secondary endpoints) show that for prevalence varying between 35% and 65%, sensitivity around 90% and specificity greater than 60% the power achieved is greater than 90% for a expected sample size between 950 and 1050 subjects under the adaptive group sequential design.

Prev.	Se	Sp	Prop. ChangeTH	Prop. Futility stop at IA1	Overall Power	Min.N	Avg.N	Max.N
0.35	0.80	0.50	0.05	0.93	0.0004	876	882	1300
0.50	0.80	0.50	0.05	0.94	0.0001	876	882	1300
0.65	0.80	0.50	0.07	0.92	0.0000	876	884	1300
0.35	0.85	0.50	0.19	0.77	0.0094	876	904	1300
0.50	0.85	0.50	0.18	0.78	0.0106	876	904	1300
0.65	0.85	0.50	0.21	0.75	0.0137	876	909	1300
0.35	0.90	0.49	0.40	0.57	0.0150	876	930	1300
0.50	0.90	0.49	0.39	0.58	0.0160	876	929	1300
0.65	0.90	0.49	0.40	0.57	0.0144	876	931	1300
0.35	0.80	0.55	0.16	0.78	0.0088	876	900	1300
0.50	0.80	0.55	0.16	0.80	0.0067	876	899	1300
0.65	0.80	0.55	0.19	0.77	0.0046	876	902	1300
0.35	0.79	0.60	0.33	0.63	0.0062	876	916	1300
0.50	0.79	0.60	0.35	0.61	0.0052	876	919	1300
0.65	0.79	0.60	0.35	0.62	0.0037	876	918	1300

Table 5-1: Simulation results under the Union Null Hypothesis for proposed group sequential design with thresholding at interim-1 and SSR at the last interim, for varying prevalence, sensitivity and specificity.

Prev.: Data generating prevalence

Se: Data generating Sensitivity

Sp: Data generating Specificity

Prop ChangeTH: Proportion of runs where threshold was changed at IA-1

Prop. Futility Stop at IA-1: Futility Futility stopping triggered at IA-1, however simulations carried out under non-binding futility

Overall Power: Power to detect at least the primary hypothesis

Min.N, Avg.N, Max.N: All calculated over 10,000 runs with non-binding futility

Prev.	Se	Sp	Prop. ChangeTH	Overall Power	Power to Reject All 3 endpoints	Min.N	Avg.N	Max.N
0.35	0.90	0.60	0.34	0.995	0.894	250	969	1300
0.45	0.90	0.60	0.33	0.993	0.903	250	946	1300
0.55	0.90	0.60	0.33	0.979	0.901	250	989	1300
0.65	0.90	0.60	0.36	0.947	0.829	250	1044	1300

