0.35	0.85	0.65	0.74	0.625	0.258	525	1091	1300
0.45	0.85	0.65	0.65	0.741	0.406	525	1100	1300
0.55	0.85	0.65	0.57	0.829	0.538	525	1105	1300
0.65	0.85	0.65	0.48	0.881	0.614	525	1103	1300
0.35	0.92	0.55	0.56	0.705	0.342	525	1082	1300
0.45	0.92	0.55	0.62	0.647	0.275	525	1079	1300
0.55	0.92	0.55	0.64	0.580	0.192	525	1070	1300
0.65	0.92	0.55	0.63	0.481	0.098	876	1054	1300
0.35	0.92	0.58	0.41	0.969	0.828	525	1026	1300
0.45	0.92	0.58	0.46	0.941	0.803	250	1050	1300
0.55	0.92	0.58	0.50	0.908	0.734	525	1080	1300
0.65	0.92	0.58	0.54	0.836	0.580	525	1089	1300

Table 5-2: Simulation results under the Intersection Alternate Hypothesis for proposed group sequential design with thresholding at interim-1 and SSR at the last interim, for varying prevalence, sensitivity and specificity.

Prev.: Data generating prevalence

Se: Data generating Sensitivity

Sp: Data generating Specificity

Prop ChangeTH: Proportion of runs where threshold was changed at IA-1

Overall Power: Power to detect at least the primary hypothesis

Min.N, Avg.N, Max.N: All calculated over 10,000 $\,$

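### The 90% power stated for a fixed design of 700 to 800 subjects is about 67% to 73% at the plan's own assumptions; 90% needs about 1,200 subjects

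*Protocol*

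**What the plan says.** Protocol 14.4 takes sensitivity 86% and specificity 60% as minimum true values, with about 35% of patients impaired, and concludes: "then a power of 90% can be achieved with 700 to 800 subjects under a fixed design". SAP 3.2 gives the same inputs, ties the claim to the joint hypothesis in its equation (1), and says that 90% "can be achieved with 700 to 800 subjects under a fixed design". Both sections then add 100 to 200 subjects for possible threshold calibration and arrive at a start of 900. SAP 3.2 caps the trial at 1,300.

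The test is fully specified:

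- **Success criterion** (Protocol 14.2): "the sensitivity is greater than 80% with a specificity greater than 50" percent.
- **Level** (SAP 3.1): each component "will be tested at one-sided 2.5% level of significance". SAP 3.10.1 states the same level for efficacy tests in general.
- **Statistic** (SAP 3.7): a one-sample Z for each component, with the variance taken at the null value; both must cross their boundaries.
- **Prevalence** (Protocol 14.3): "The targeted prevalence of swallow safety problems using THIN-Ba (primary endpoint) is between 0.3 and 0.4".

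**The concern.** Sensitivity is estimated only in patients whom VFSS classifies as impaired. At 35% prevalence that is roughly one third of the sample, and the margin to detect is six percentage points (86% against 80%). A few hundred patients looks too few for 90% power on that comparison.

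The sentence matters because it is the only derivation given for the 900 start. Ethics committees, regulators and the data monitoring committee would read it as a 10% risk of missing a device that performs as assumed.

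The SAP's simulations do not cover the case. The text of Appendix 5.1 claims high power for "sensitivity around 90% and specificity greater than 60% the power achieved is greater than 90" percent. Table 5-2 ("Simulation results under the Intersection Alternate Hypothesis for proposed group sequential design") uses sensitivities 0.85, 0.90 and 0.92. It has no row at 0.86 and none at prevalence 0.30.

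**Working it through.** **Inputs.** Null values 0.80 and 0.50 (Protocol 14.2, SAP 3.1). True values 0.86 and 0.60, prevalence 0.35 (Protocol 14.4, SAP 3.2). One-sided 2.5% for each component (SAP 3.1). Null-variance Z, both required (SAP 3.7).

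**Formula.** For n subjects, null p0 and true value p1:

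power = Φ[ (√n (p1 − p0) − 1.96 √(p0(1 − p0))) / √(p1(1 − p1)) ]

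Impaired and unimpaired patients are separate groups, so joint power is the product of the two. For sensitivity, √(0.8 × 0.2) = 0.4 and √(0.86 × 0.14) = 0.347. For specificity, √(0.5 × 0.5) = 0.5 and √(0.6 × 0.4) = 0.490.

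**Attempt to reproduce 90%, at N = 700.**

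- Impaired: 0.35 × 700 = 245. Sensitivity: (√245 × 0.06 − 1.96 × 0.4)/0.347 = (0.939 − 0.784)/0.347 = 0.447, and Φ(0.447) = 0.673.
- Unimpaired: 455. Specificity: (√455 × 0.10 − 1.96 × 0.5)/0.490 = (2.133 − 0.980)/0.490 = 2.354, and Φ(2.354) = 0.991.
- Joint: 0.673 × 0.991 = 0.67.

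The stated figure is not reproduced. The same steps at other sizes:

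| N | Impaired / unimpaired | Sensitivity | Specificity | Joint |
|---|---|---|---|---|
| 700 | 245 / 455 | 0.673 | 0.991 | 0.666 |
| 800 | 280 / 520 | 0.737 | 0.996 | 0.734 |
| 900 | 315 / 585 | 0.791 | 0.998 | 0.790 |

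**Size needed for 90%.** For sensitivity, n = ((1.96 × 0.4 + 1.2816 × 0.347)/0.06)² ≈ 419 impaired, and 419.3/0.35 ≈ 1,198 in total. The joint requirement is about 1,199. Specificity alone would need only about 398 subjects in total.

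**Exact check.** Exact binomial power of the same rule, with the number impaired allowed to vary around 35%, is 0.672, 0.737 and 0.791 at 700, 800 and 900, and 0.898 at 1,200. The normal approximation is not the cause.

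**Prevalence across the target range (SAP test, joint power).**

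| Prevalence | N = 700 | N = 800 | N = 900 | N for 90% |
|---|---|---|---|---|
| 0.30 | 0.594 | 0.661 | 0.719 | about 1,398 (above the cap) |
| 0.35 | 0.666 | 0.734 | 0.790 | about 1,199 |
| 0.40 | 0.726 | 0.792 | 0.844 | about 1,051 |

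**Other methods.** The documents do not say which formula produced 700 to 800, so I tried others.

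- Wald variance, power = Φ(√n (p1 − p0)/√(p1(1 − p1)) − 1.96), at prevalence 0.35: 0.766, 0.822 and 0.865 at 700, 800 and 900, with 90% near 1,006. At prevalence 0.40 and N = 800 it gives 0.87.
- Arcsine: 90% at 1,169. Null variance throughout: 90% at 1,335.
- The closest match uses one-sided 5% with Wald variance (0.853 at 700, 0.893 at 800, 90% at 822). That is neither the plan's level nor its test. One-sided 5% with the SAP's own statistic gives 0.788 to 0.839.

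**Sensitivity that would make the sentence true.** With the SAP test at prevalence 0.35 and specificity 0.60, joint power of 90% needs a true sensitivity of 0.878 at 700 or 0.873 at 800.

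**The case against.** The strongest reply is that the fixed design is only a reference point. The trial that will run is group sequential, may restart after a threshold change, and may grow to 1,300 through re-estimation, which the SAP introduces because the parameters are uncertain. The SAP is also fairly open about low power: Table 5-2 shows 0.625 at sensitivity 0.85, specificity 0.65 and prevalence 0.35, and 0.995 at 0.90 and 0.60. A careful reader of the appendix would not expect 90% everywhere.

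That bears on the consequences but not on the sentence, which claims 90% for a fixed design and is false for one. Nor do I find that re-estimation clearly restores 90%. A simulation of the three-look design with the threshold unchanged (40,000 runs, primary endpoint only, growth to at most 1,300) gives about 0.78 if both conditional powers must lie in the promising zone and 0.81 to 0.82 if the lower one governs. It assumes look sizes of 200/550/900, 250/525/876 or 250/600/900, because the documents do not fix them. It covers one branch only and says nothing about a restarted trial, which SAP 3.5 powers afresh. The conclusion does not depend on it. The 0.85/0.65 row likewise fits low power in this region but does not verify the 0.86 figure.

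A second reply is that 86% and 60% are minimum values. A power claim made for a minimum has to hold at that minimum.

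Two points stand. The size of the error depends on the method: 67% to 73% with the SAP's test, 77% to 82% with Wald variance. And once the 90% is withdrawn, the step from 700–800 to 900 no longer has a stated power behind it, so that step needs rewording too.

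**Conclusion.** The stated power is wrong in both documents and must be corrected. At sensitivity 86%, specificity 60%, prevalence 35% and one-sided 2.5% for each component, the SAP's test has about 67% joint power with 700 subjects and 73% with 800. That is 17 to 23 percentage points below the claim, and a miss risk of 27% to 33% in place of 10%. A fixed 900 gives 79%.

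No method tried at the plan's significance level reaches 90% at 700 to 800, and the best value at N = 800 within the target prevalence range is 0.79 (SAP test) or 0.87 (Wald). Confidence is high, because every input is in the documents. The conclusion concerns the fixed-design statement only; the power of the full adaptive trial at these assumptions is not shown in the SAP.

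**What to change.** In Protocol 14.4 and SAP 3.2, name the test and do one of the following:

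- State that at 86% sensitivity, 60% specificity and 35% prevalence a fixed design has about 67% power with 700 subjects, 73% with 800 and 79% with 900, and reaches 90% near 1,200.
- Keep 90% and state that it assumes a true sensitivity of about 87.8% at 700 subjects or 87.3% at 800.

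Reword the next sentence in each document so that the 900 start rests on whichever statement is chosen and the accepted power is explicit. Add rows to Table 5-2 for sensitivity 0.86 and specificity 0.60 at prevalence 0.30, 0.35 and 0.40. The 0.35 row answers the point directly; the other two cover the target range.

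The cost is a short rewording in each document and three more simulation scenarios. The stated power, or the sensitivity it assumes, becomes less favourable. The 900 start and the 1,300 cap can stay.
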